11.6.1.3 Sensitivity Analyses

Inherent in the primary endpoint analysis described above are several implicit assumptions that can possibly affect the generalizability of immunogenicity. There are four assumptions that are important to mention. The primary analysis assumes that the impact on the immunogenicity conclusion of early discontinuations, important protocol deviations, less than full treatment duration and patterned missing data is negligible. Although the scientific rationale to make these assumptions is reasonable, sensitivity analyses for the primary endpoint of immunogenicity to assess the impact of these effects are planned, as follows.

- 1) **Composite Strategy:** Subjects in the SS with the intercurrent event of discontinuing treatment will be considered as having a treatment-induced AIA. Results of assessment after the end of treatment are excluded from the analysis. The imputation approach as described in Table 4 will be used for missing data. This sensitivity analysis will examine the assumption that results were not impacted by the discontinuation of treatment (as these will be imputed as positive immune response).
- 2) **Per Protocol Analysis Set (PPS):** Subjects with any important protocol deviations (as defined in Section 11.3) will be excluded from the analysis. For subjects in the PPS, the imputation approach as described in Table 4 for primary analysis will be followed. In the primary analysis, subjects with important protocol deviations could falsely draw the estimated treatment difference closer. Exclusion of these subjects in this sensitivity analysis will help assess the magnitude, if any, of this effect.
- 3) **SS - Completers:** This analysis will not use any imputation of missing data. Only subjects with valid baseline and visit Week 12 and Week 26 assessments conducted within the required visit window (visit Week 12 \pm 1 week and visit Week 26 \pm 4 weeks, respectively) and who had treatment until visit Week 26 will be used for the analysis. Subjects with less than a full treatment duration could

underestimate the proportion of subjects reporting positive immune response. By including only completers, as in this sensitivity analysis, this estimated treatment difference is determined only by subjects whose treatment duration was full.

- 4) Per Protocol Analysis Set 2 (PPS2) - Subjects with any immunogenicity-interfering important protocol deviations (IIPD; as defined in Section 11.3) will be excluded from the analysis. For the subjects in the PPS2, the imputation approach as described in Table 4 for primary analysis will be followed. In the primary analysis, subjects with immunogenicity-interfering important protocol deviations could falsely draw the estimated treatment difference closer. Exclusion of these subjects in this sensitivity analysis will help assess the magnitude, if any, of this effect.
- 5) ERIPD Interaction Analysis for immunogenicity – To assess the impact of eligibility related important protocol deviations on the treatment effect for immunogenicity, this analysis will be carried out using an extended model of the main analysis, by including ERIPD (yes/no) and treatment by ERIPD interaction as factors. The interaction parameter estimate, 90% CI and p-value will be presented with number and percentage of subjects in each ERIPD category under each treatment arm.

All these sensitivity analyses will be conducted as described for the primary analysis, using the same margins from the primary analysis.

Additional analyses examining the development of treatment-induced AIA at Week 26 in the following subgroups using the SS with imputation as described in Table 4 for primary analysis will be presented in a forest plot:

- Gender (Male versus Female)
- Age (< 65, versus ≥ 65 years old)
- Race (white versus non-white)
- BMI (Obese versus Non-obese)
- Menopausal Status (Pre- versus post-)
- Dosing Regimen (Twice daily (BID) Dosing at least once versus daily (QD) Dosing)
- Previous Exposure to Lantus® (No previous exposure versus previous exposure (within 6 months prior to study initiation))

11.6.1.4 Multiplicity

Hierarchical testing strategy will be used to account for multiplicity. Equivalence in efficacy will only be demonstrated if equivalence in immunogenicity is demonstrated.

11.6.2 Secondary Immunogenicity Endpoints

All analyses will include on and after study treatment AIA data up to visit Week 26.

11.6.2.1 Subjects with Negative Anti-Insulin Antibodies at Baseline Who Develop Newly Confirmed Positive Anti-Insulin Antibodies

The percentage of subjects in each treatment group with negative AIA at baseline who develop newly confirmed positive AIA after baseline and up to visit Week 26 will be summarized in proportions. The difference in proportions will be estimated along with the corresponding 90% CI in the subset of SS using a logistic regression model.

Missing data will be imputed as described for the primary endpoint in Table 4.

Sponsor: Gan & Lee Pharmaceuticals, USA Corporation
Protocol no: GL-GLAT2-3002

Statistical Analysis Plan
Version Date: 16-Nov-2020

11.6.2.2 Subjects with Important Increase in AIA Titers

The percentage of subjects in each treatment group with confirmed positive AIA at baseline who develop important increase (at least a 4-fold increase) in titers (defined in Section 7.2) up to visit Week 26 will be compared using an difference in proportions. The difference in proportions will be estimated along with the corresponding 90% CI in the subset of SS (with positive AIA at baseline) using a logistic regression model with treatment as the only independent variable in the model.

11.6.2.3 Change in Anti-Insulin Antibody Titer

The change from baseline in AIA titers at visit Week 12 and visit Week 26 will be summarized descriptively in subjects with confirmed positive AIA at baseline. Though not specified in the protocol, this analysis is planned for the subset of subjects with confirmed positive AIA only.

11.6.2.4 Subjects with Confirmed Positive Anti-Insulin Antibodies Who Develop Newly Confirmed Neutralizing AIA

The percentage of subjects in each treatment group with confirmed neutralizing AIA after baseline and up to visit Week 26 will be compared using difference in proportions. The difference in proportions will be estimated along with the corresponding 90% CI in the SS using a logistic regression model with treatment as the only independent variable in the model.

Missing data will not be imputed, the percentages will be based on the subjects with documented confirmed positive AIA after baseline and up to visit Week 26.

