6.3 Other Secondary Endpoints

6.3.1 Immunogenicity

- The percentage of subjects in each treatment group with negative AIA at baseline who develop confirmed positive AIA after baseline and up to visit Week 26
- The percentage of subjects in each treatment group with confirmed positive AIA at baseline and at least a 4-fold increase in titers after baseline and up to visit Week 26
- The mean change from baseline in each treatment group in AIA titers after baseline and up to visit Week 26. Though not specified in the protocol, this analysis is planned for the subset of subjects with confirmed positive AIA at baseline
- The percentage of subjects in each treatment group with confirmed positive AIA after baseline and up to visit Week 26 who develop any anti-insulin neutralizing antibodies after baseline and up to visit Week 26
- The percentage of subjects in each treatment group with confirmed positive AIA after baseline and up to visit Week 26. This summary is planned to include all subjects regardless of subject's status of AIA at baseline

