7.1 General

1) Actual Treatment

The actual treatment received is defined as the IP treatment the subject received during the study, regardless of the treatment the subject was allocated to by randomization. If a subject receives both Gan & Lee Insulin Glargine Injection and Lantus® during the study period for whatever reason, then the actual treatment will be based on the treatment taken on the majority of days during the study.

2) Assessment after EOT

Assessment after EOT is defined as AIA/HbA1c assessment documented after date of EOT visit. If date of EOT visit is missing it is defined as assessment documented after date of last dose of IP + 1 day (to consider assessments of subjects who perform the visit assessment before daily dose of IP).

3) Average Daily Dose of IP

Average Daily Dose is defined as captured on the Average Daily Dose of Study Drug CRF page.

4) Baseline

For each endpoint of interest, unless otherwise noted, the study baseline is defined as the last non-missing assessment taken prior to or on the date of the first dose of study IP. For subjects whose treatment assignment is randomly assigned but not dosed after the randomization visit, the baseline is defined as the last non-missing assessment prior to or on the date of randomization.

5) Change from Baseline

Change from baseline is defined as (value at post-baseline visit – value at baseline).

6) Completer Week 26

A subject is defined as a Completer Week 26 if the answer to the question "Did the subject complete the study?" is "Yes" on the End of Study CRF page and who received IP for at least 22 weeks.

7) Dates of First and Last Dose

The date of first dose of IP is defined as the date of first dose of IP documented on the First Dose of Study IP CRF page and the date of last dose of IP is defined as the date of last dose of IP documented on the End of Study 2 CRF page. If no date of first dose of IP is available, the date of randomization will be selected as the date of first dose of IP. If no date of last dose of IP is available, the date of completion/discontinuation documented on the End of Study CRF page will be selected as the date of last dose. If date of last dose of IP is not available and subject is lost to follow up based on End of Study CRF page, date of last scheduled visit or date of last telephone contact where an average daily dose is recorded, will be used as the date of last dose of IP.

8) Diabetes Disease Duration

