7.2 Immunogenicity

Blood samples taken from the subjects throughout the study will undergo three-tiered testing. Initially, they will be screened for AIA. Samples with a result falling above a pre-specified threshold will be deemed 'screened positive', otherwise they will be reported as 'negative'. The samples that were "screened positive" will be subsequently tested in the confirmatory assay and will be reported as either 'negative' or 'confirmed positive'. Finally, if found to be 'confirmed positive', samples will then undergo AIA titer analysis in which the sample is diluted until it crosses the specific cut-point, which allows for semi-quantification. In addition, the confirmed positive samples will be tested for neutralizing activity within the neutralizing assay.

1) Confirmed Positive AIA

A subject is deemed to have confirmed positive AIA at a timepoint if both, the screening assay and the confirmatory assay at that timepoint have a positive result, as described above. A subject can have a confirmed positive AIA at any timepoint, including baseline.

2) Negative AIA

A subject is deemed to have negative AIA at a time point if the screening assay at that time point has a negative result. A subject can have a negative AIA at any time point, including baseline.

3) Newly Confirmed Anti-insulin Neutralizing Antibody (NAb)

A subject is deemed to have developed newly confirmed NAb if the subject has a negative AIA at baseline and a confirmed positive AIA after baseline and up to visit Week 26 and has developed anti-insulin neutralizing antibodies after baseline and up to visit Week 26 at any post-baseline measurements.

4) Newly Confirmed Positive AIA

A subject is deemed to have developed a newly confirmed positive AIA if the subject has a negative AIA at baseline, and a confirmed positive AIA after baseline and up to visit Week 26.

5) Important increase in AIA titers

An important increase in AIA titers is defined for subjects who have a (1) confirmed positive AIA at baseline and (2) a non-missing baseline and post-baseline titer analysis, and the ratio of post-baseline titer to baseline titer is greater than or equal to 4.

6) Treatment-Induced AIA

Treatment-Induced AIA (primary endpoint) is defined as one of the following:

- Newly Confirmed post-baseline positive AIA (in baseline negative)
- Important increase in AIA titers (in baseline positive and with 4-fold increase in titers; post-baseline-to-baseline ratio.)

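### AIA titer change is summarised as raw differences, and no rule gives a value to baseline-positive subjects who later test negative

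*SAP*

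**What the plan says.** SAP 6.3.1 lists as an other secondary endpoint "The mean change from baseline in each treatment group in AIA titers after baseline and up to visit Week 26". SAP 11.6.2.3 states the analysis: "The change from baseline in AIA titers at visit Week 12 and visit Week 26 will be summarized descriptively", and limits it to a subset, "in subjects with confirmed positive AIA at baseline". Protocol 12.9.1.3 plans the same descriptive summary in the same subset. Neither text gives a log or fold-change scale.

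The general definition in SAP 7.1 therefore applies: "Change from baseline is defined as (value at post-baseline visit – value at baseline".

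SAP 7.2 explains where a titer comes from: "if found to be 'confirmed positive', samples will then undergo AIA titer analysis in which the sample is diluted until it crosses" the cut-point, a procedure "which allows for semi-quantification". Samples that fail the screening or the confirmatory assay are reported as negative and are not titered. The same section defines an important increase multiplicatively: "the ratio of post-baseline titer to baseline titer is greater than or equal to 4".

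The opening of SAP section 11 lists the statistics for continuous variables: n, mean, SD, median, quartiles, minimum and maximum.

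**The concern.** Two features of this summary do not fit the measurement.

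- **Scale.** A dilution titer moves in multiples, and the companion analysis in SAP 11.6.2.2 treats it that way. The change summary treats it additively, so the same fold change weighs more the higher the starting titer.
- **Who is left in.** A baseline-positive subject who turns negative has the outcome of most interest on the favourable side, yet has no titer at that visit. If nothing is substituted, the subject leaves the summary because of the outcome.

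At stake is interpretation. Comparing titer change between the arms is a stated secondary objective (Protocol 7.2.1, SAP 4.2.1), and immunogenicity is the trial's primary question. Readers will set the two arms side by side even without a test. If different shares turn negative in the two arms, that reading is distorted.

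**Working it through.** The documents give no expected value, SD or sample size for titer change, so there is no planned figure to reproduce. They also give no count of baseline-positive subjects, titer distribution, dilution factor or share turning negative. All titers below are assumed, for illustration only.

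**1. Scale.** Change = post-baseline − baseline. A doubling from 10 adds 10; a doubling from 640 adds 640. The second counts 640/10 = 64 times as much, although both are one log2 step.

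**2. Is there a rule for samples that turn negative?**
- SAP 11.6.2.1 and 11.6.2.5 refer to the imputation in Table 4. SAP 11.6.2.4 says missing data are not imputed. SAP 11.6.2.3 says neither.
- Table 4 (SAP 11.6.1.2) assigns a yes/no status, not a titer.
- The lower-limit substitution in SAP 11.8.3 is for laboratory test results; AIA is not among the assessments grouped there.
- Definition 5 of SAP 7.2 requires titers at both times, so the SAP foresees that some will be absent.

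No stated rule keeps these subjects in.

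**3. Direction of the shift.** If k of n subjects are dropped, then

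mean(remaining) − mean(all) = (k/n) × [mean(remaining) − mean(dropped)].

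With any substitute no higher than the lowest titer, the change of each dropped subject is zero or negative. The shift is therefore upward unless the subjects still titered fell, on average, by more. Its size needs k/n and the dropped subjects' mean change, and the documents give neither.

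**4. Worked example (assumed).** Twenty baseline-positive subjects: eight at titer 10, eight at 20, four at 40. One rises from 10 to 1280, six turn negative (two from each level), and 13 are unchanged.

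Plain reading, negatives dropped, n = 14:
- Raw mean = (1280 − 10)/14 = +90.7. Without the one riser it is 0/13 = 0.0. The median is 0.
- Log scale: log2(1280/10) = 7; 7/14 = 0.5; geometric mean fold change = 2^0.5 = 1.41.

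Negatives kept at an assumed value, n = 20:

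| Value for negatives | Sum of log2 change, six negatives | Mean log2 change, all 20 | Geometric mean fold change | Raw mean |
|---|---|---|---|---|
| 1 | −25.93 | (7 − 25.93)/20 = −0.95 | 0.52 | +56.8 |
| 5 | −12 | (7 − 12)/20 = −0.25 | 0.84 | +58.0 |
| 10 | −6 | (7 − 6)/20 = +0.05 | 1.04 | +59.5 |

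Check of step 3 with value 5: the dropped mean is −12/6 = −2, and (6/20) × [0.5 − (−2)] = 0.75, which equals 0.5 − (−0.25).

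Keeping the negatives can reverse the direction on the log scale, and the value chosen for them matters.

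**5. Simulation (assumed).** Baseline log2 steps above a lowest titer of 10: exponential with mean 1.5, rounded down. Log2 change: SD 1.5, rounded to whole steps. Number of baseline-positive subjects: 30 to 100. Negatives are kept one step below the lowest titer.

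| True log2 shift | Share turning negative | Mean log2 change, remaining titers | Mean log2 change, negatives kept |
|---|---|---|---|
| 0 | 23% | +0.52 | about +0.12 |
| −0.5 | 32% | about +0.18 | about −0.29 |
| −1 | 42% | about −0.15 | about −0.65 |

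In these runs the remaining titers read about 0.4 to 0.5 log2 steps too high relative to keeping the negatives. The largest 5% of observed raw changes carry about 40% to 57% of the total absolute raw change.

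**The case against.** The strongest reply is that this is one descriptive table among several, and much of the substance is covered elsewhere.

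- **No inference depends on it.** There is no test, interval or margin, and it lies outside the hierarchy in SAP 11.6.1.4. This stands in full. A reader might infer that an equivalence conclusion is at risk; it is not.
- **Robust statistics are planned.** A reader might infer that a few high titers drive the whole endpoint. They can dominate the mean and SD, but the median and quartiles resist them and the maximum exposes them. This stands. The median does not, however, bring back subjects who have no titer.
- **Exclusion of negatives is inferred from silence.** The SAP does not say they are left out, and the table shells (SAP Appendix 3) are a separate document not available here; they may assign a value. This stands, so the supportable statement is that no rule keeps them in.
- **The ratio scale is already used.** The 4-fold analysis in SAP 11.6.2.2 has a 90% CI for the arm difference. This stands for rises; it says nothing about falls. Post-baseline positivity (SAP 11.6.2.5) reflects loss of positivity only in part, since one positive result at any time up to Week 26 counts.
- **The n per visit shows absent titers.** True, but it does not separate a negative result from a missing sample.
- **The log scale has its own weakness.** In the example, the 1.41 also comes from the single riser, and substituting a value for negatives can set the direction. Both points stand. They are the reason to show the count of negatives and a second substitute value, and a confidence interval around substituted values would add little.

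**Conclusion.** The concern holds in a limited form. The planned summary uses raw differences for a dilution-based measure. No stated rule keeps in the baseline-positive subjects who later test negative. On a plain reading they drop out, and the summary of the remaining titers is shifted upward, provided those remaining did not fall by more on average.

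The size cannot be computed from the documents. The figures above show only what is possible under assumed titers: a raw mean moved from 0.0 to +90.7 by one subject, and a geometric mean fold change of 1.41 without the negatives against 0.52 to 1.04 with them.

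A reader might also infer that the subset is small and the estimate very unstable. The documents give no count of baseline-positive subjects and no titer distribution, so neither claim is supported.

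This is a minor point: a better method for a stated secondary objective, with no bearing on the primary or key secondary conclusion.

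**What to change.** In SAP 11.6.2.3:

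1. Report log2 titer change, back-transformed to a geometric mean fold change, by arm and visit, alongside the median and quartiles already planned.
2. Show the number and percentage of baseline-positive subjects who turn negative, by arm and visit, separately from those with no sample.
3. Prespecify the value given to those negatives, and repeat the summary with a second value as sensitivity, because the result depends on it.

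If the table shells already assign a value, state it in the SAP.

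The cost is one transformation, one substitution rule and a few extra table rows. No new data are needed and no other analysis changes. The downside is that the substitute value is a convention, which is why the counts and the second value should stand beside it.

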11.6.2.5 Subjects with Confirmed Positive Anti-Insulin Antibodies

The percentage of subjects in each treatment group with confirmed positive AIA after baseline and up to visit Week 26 will be compared using difference in proportions. The difference in proportions will be estimated along with the corresponding 90% CI in the full SS using a logistic regression model with treatment as the only independent variable in the model.

Missing data will be imputed as described for the primary endpoint in Table 4.

11.7 Efficacy Analyses

11.7.1 Key Secondary Endpoint

An overview of planned analyses for the key secondary endpoint of change from baseline in HbA1c, including sensitivity analyses, is provided in Table 5 below.

Table 5: Overview of key secondary endpoint analyses

Analysis	Population used	Analysis Details	Section reference
1. Main analysis	Full analysis set	Treatment Policy Estimand - ANCOVA using MI under the assumption of MNAR; this analysis uses unscheduled HbA1c results from discontinued subjects to impute missing in each treatment arm.	Section 11.7.1.1 Change from Baseline in HbA1c at 26 weeks

Gan & Lee Pharmaceuticals USA

PRA HEALTH SCIENCES

 Sponsor: Gan & Lee Pharmaceuticals, USA Corporation
 Protocol no: GL-GLAT2-3002

 Statistical Analysis Plan
 Version Date: 16-Nov-2020

Analysis	Population used	Analysis Details	Section reference
2. Sensitivity analysis	Per protocol analysis set	ANCOVA using MI under the assumption of MNAR; this analysis uses the same approach for imputation as the main analysis. Used to assess the robustness of main analysis to important deviations from the protocol.	Section 11.7.1.3 Sensitivity Analyses - PPS
3. Sensitivity analysis	Full analysis set of completers	ANCOVA without imputation. This analysis is used to assess the robustness of main analysis to subjects lost to follow-up.	Section 11.7.1.3 Sensitivity Analyses - FAS completers
4. Sensitivity analysis	Per protocol analysis set 3	ANCOVA using MI under the assumption of MNAR; this analysis uses the same approach for imputation as the main analysis. In the main analysis, subjects with efficacy-interfering deviations could falsely draw the estimated treatment difference closer. Exclusion of these subjects in this sensitivity analysis will help assess the magnitude, if any, of this effect.	Section 11.7.1.3 Sensitivity Analyses - Per Protocol Analysis Set 3
5. Sensitivity analysis	Full analysis set	Treatment Policy Estimand – MMRM will include all longitudinal HbA1c data points measured.	Section 11.7.1.3 Sensitivity Analyses - Mixed Model Repeated Measure
6. Sensitivity analysis	Full analysis set	ANCOVA using MI under the assumption of MNAR. This analysis uses unscheduled HbA1c results from discontinued subjects to impute missing in each treatment arm, with the addition of the term of presence/absence of ERIPD main effect and an interaction term of treatment*ERIPD.	Section 11.7.1.3 Sensitivity Analyses – ERIPD Interaction Analysis for Efficacy
7. Sensitivity analysis	Full analysis set	ANCOVA using MI under the assumption of MNAR in each treatment arm for the following subgroups: Gender (male versus female), Age (< 65, versus ≥ 65 years old), Race (white versus non-white), BMI (Obese versus Non-obese), Menopausal Status (Pre- versus post-), Eligibility Criteria Met (Presence of an eligibility-related important protocol deviation versus no presence of an eligibility-related important protocol deviation).	Section 11.7.1.3 Sensitivity Analyses – Subgroup analyses
8. Tipping point analysis	Full analysis set	ANCOVA using MI under progressively severe departures from missing at random (MAR) assumption (i.e. MNAR assumption).	Section 11.7.1.3 Sensitivity Analyses - Tipping point analysis

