Eligibility-related important protocol deviations are important protocol deviations violating any inclusion or exclusion criteria (refer to Appendix 4 for details). This indication will be used in sensitivity analyses for immunogenicity, efficacy, and safety measures to evaluate the impact of these important deviations.

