In addition, the same non-inferiority test with a margin of 0.3% will be performed.

The 95% CI will be estimated using a pattern mixture model that uses multiple imputation analyzed using ANCOVA with treatment included as a fixed effect and baseline HbA1c included as a covariate. Separately in each treatment group, the imputation will use outcomes in subjects who discontinued treatment prior to Week 26 but returned to provide a visit Week 26 HbA1c sample (labeled as the unscheduled) to impute outcomes in subject without actual visit Week 26 recorded results under the MNAR assumption. No imputation will be performed for missing baseline HbA1c.

Analysis of HbA1c will follow a hierarchical testing strategy: first, non-inferiority will be tested using a margin of 0.4%, and only if this test is significant, then non-inferiority will be tested using a margin of 0.3%.

Sponsor: Gan & Lee Pharmaceuticals, USA Corporation
 Protocol no: GL-GLAT2-3002

Statistical Analysis Plan
 Version Date: 16-Nov-2020

Non-inferiority will be assessed based on the 95% CI; no p-values will be computed. Change from baseline in HbA1c between Gan & Lee Glargine Injection and Lantus® will be considered non-inferior if the 95% CI is below the margins of 0.4 and 0.3%, respectively.

For both, FDA and EMA submissions, to estimate the CI of the difference in HbA1c, the pattern-mixture model will be fitted using the SAS® procedure "MIXED" for FAS. A sample SAS code fragment is provided below for reference (note: actual seeds to be used in the analysis are presented below):

```
proc mi data=<data> nimpute=50 seed= 359648 out=<out_data>;
  by trt;
  class unscheduled;
  monotone reg(Week26_HbA1c=base_HbA1c);
  mnar model(Week26_HbA1c / modelobs = (unscheduled = '1'));
  var base_HbA1c;
run;
```

In between these steps, the data will be transposed and then the change from baseline at visit Week 26 will be calculated.

```
proc mixed data=<out_data> out=<lsmeans>;
  by _imputation_;
  class trt;
  model CFB_HbA1c_26 = trt base_HbA1c / ddfm=kr;
run;
proc mianalyze data=<lsmeans>;
  by effect;
  modeleffects estimate;
  stderr;
run;
```

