- 4) Mixed model repeated measure (MMRM): this sensitivity analysis will include all post-baseline HbA1c measures from each time point as the dependent variable. The independent variables in the model include fixed effects for treatment assignment (2 levels), time (3 post-baseline times), treatment-by-time interaction, and covariate terms for the baseline HbA1c score and baseline HbA1c score-by-time interaction (which allows the effect of baseline covariate parameter to change over time). An unstructured covariance matrix will be used to model the inter-dependencies among the repeated measures. However, if the model does not converge, an alternative covariance matrix will be used which is appropriate for the repeated measurements (e.g., first-order autoregressive). Given the missing data, the Kenward-Roger approximation will be used for calculating the denominator degrees of freedom and adjusting standard errors. If a structured variance-covariance matrix is used, sandwich estimator will be used to estimate the variance of the treatment effect estimate. The FAS will be used to generate the results. (Table 5, Analysis 5)

The SAS code to be used for the repeated measure model is:

```
Proc mixed data=<data>;
  class trt visit subject;
  model HbA1c = trt
        visit
        trt*visit
        base_HbA1c
        base_HbA1c*visit
        / solution ddfm=kr;
  repeated visit / subject = subj type=un;
  lsmeans treatment*visit / pdiff cl;
run;
```

- 5) ERIPD Interaction Analysis for Efficacy – To assess the impact of eligibility related treatment effect on efficacy, this analysis will be a repeat of the main analysis with the addition of the term of presence/absence of ERIPD main effect and an interaction term of treatment*ERIPD. The parameter estimate of the interaction term, 90% CI and p-value will be presented with least square means estimated for each ERIPD group under the treatment arms. (Table 5, Analysis 6)

Additional analysis examining the change from baseline in HbA1c at visit Week 26 in the following subgroups will be presented in a table and a forest plot, by treatment groups but not overall. Missing outcomes were imputed separately in each treatment group using outcomes in subjects who completed the study. These analyses will be conducted according to the FDA submission approach (i.e. 90% CI and 0.4% margin) with MI for the FAS (Table 5, Analysis 7):

- Gender (Male versus Female)
- Age (< 65 versus ≥ 65 years old)

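### HbA1c Analysis 6 tests a treatment-by-ERIPD interaction, but the imputation it reuses appears to omit ERIPD, so the interaction estimate can be biased

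*SAP*

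**What the plan says.** SAP Section 11.3 gives the purpose of the ERIPD flag: "This indication will be used in sensitivity analyses for immunogenicity, efficacy, and safety measures to evaluate the impact of these important deviations". For HbA1c, Section 11.7.1.3 item 5 (Table 5, Analysis 6) says "this analysis will be a repeat of the main analysis with the addition of the term of presence/absence of ERIPD main effect" and a treatment-by-ERIPD interaction. On output it says: "The parameter estimate of the interaction term, 90% CI and p-value will be presented". The Table 5 row gives the same analysis "with the addition of the term of presence/absence of ERIPD main effect and an interaction term of treatment*ERIPD", but is looser. It describes using returned discontinuers "to impute missing in each treatment arm, with the addition of the term of presence/absence of ERIPD main effect", without saying which model takes the added terms.

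The only imputation model specified for the main analysis is the sample code in Section 11.7.1.1. It runs separately by arm, regresses on baseline alone ("monotone reg(Week26_HbA1c=base_HbA1c") and takes its donors from subjects who stopped treatment but returned ("mnar model(Week26_HbA1c / modelobs = (unscheduled = '1"). ERIPD appears nowhere in it.

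Analysis 7 covers subgroups, one of which is whether eligibility criteria were met. Table 5 describes it as "ANCOVA using MI under the assumption of MNAR in each treatment arm for the following subgroups". The text of Section 11.7.1.3 says its missing outcomes are imputed by arm from subjects who completed the study. Neither place says whether the subgroup variable enters the imputation.

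**The concern.** An imputation model should contain the terms that the analysis model is meant to estimate. Here, two subjects in the same arm with the same baseline HbA1c, one with an ERIPD and one without, draw their missing Week 26 values from the same distribution. Their imputed records therefore contribute no ERIPD effect and no treatment-by-ERIPD interaction. The ANCOVA then averages observed records, which carry any such effect, with imputed records, which cannot.

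What is at stake is how far one pre-specified sensitivity result can be trusted. The analysis exists to show whether ineligible subjects altered the treatment comparison, and its estimate would usually be pulled toward reassurance. Two statements make missing data a live issue. Section 5.1 reports more early discontinuation than expected. Section 11.2 allows ineligibility as a withdrawal sub-category, so missingness could be concentrated in ERIPD subjects.

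**Working it through.** **The plan's own figure.** No power or precision is stated for HbA1c or for this interaction. The design figure given is the primary-endpoint power (Section 5.1: AIA rate 30%, margin 12%, 275 per arm). SE = √(2 × 0.30 × 0.70 / 275) = 0.0391, and power = 2Φ(0.12/0.0391 − 1.645) − 1 = 84.6%, against about 85% stated. It reproduces, but has no bearing on this point beyond fixing n.

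**Inputs.** From the SAP: 275 per arm, by-arm imputation on baseline HbA1c from returners, and a 90% CI for the interaction. Assumed, because not given: 5% to 30% missing at Week 26, 20% of subjects with an ERIPD, returners 6% or 10% of each arm, residual SD 0.9 or 1.0, and a true interaction of 0.40 (the size of the HbA1c margin).

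**Closed form.** Let m1 and m0 be the missing fractions with and without an ERIPD, the same in both arms, and π the ERIPD share among donors. If the ERIPD effect is the same in missing and observed subjects, the share of the interaction retained is

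1 − m1(1 − π) − m0π,

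which is 1 − m when m1 = m0 = m.

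| Missing | Expected from 0.40 | Simulated, as written | Simulated, ERIPD added, returner donors only |
|---|---|---|---|
| 5% | 0.38 | 0.38 | 0.40 |
| 10% | 0.36 | 0.35 | 0.40 |
| 20% | 0.32 | 0.32 | 0.40 |
| 30% | 0.28 | 0.31 | 0.41 |

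Settings: 10% returners, SD 1.0, 20 imputations (the SAP uses 50), 400 runs as written and 300 with ERIPD added. In the as-written runs at 30% missing, the mean before any deletion happened to be 0.43, and 0.7 × 0.43 = 0.30, so the last row agrees too. With 6% returners and SD 0.9, the as-written mean at 20% missing was 0.31.

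**More missingness in ERIPD subjects.** At 35% against 15%: 1 − 0.35 × 0.8 − 0.15 × 0.2 = 0.69, giving 0.28 (simulated 0.28). At 40% against 15%: 0.65, giving 0.26 (simulated 0.25).

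**Unequal missingness between arms.** Take an ERIPD main effect of 0.5, with 30% missing on the test product and 10% on Lantus. With a true interaction of 0, the expected estimate is 0.7 × 0.5 − 0.9 × 0.5 = −0.10 (simulated −0.10). With a true −0.20 it is 0.7 × 0.3 − 0.9 × 0.5 = −0.24 (simulated −0.25), further from zero than the truth.

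**Effect present only on treatment.** At 20% missing and 6% returned, 74% are on treatment, so the true full-set interaction is 0.40 × 0.74 = 0.30. The plan as written gives 0.28 to 0.30 in simulation, close to unbiased. A model with ERIPD fitted to all observed values has an ERIPD term of about 0.40 × 0.74/0.80 = 0.37 and so gives 0.30 + 0.20 × 0.37 = 0.37 (simulated 0.35 to 0.38), too large.

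**Donor count.** Returners with an ERIPD per arm: 275 × 0.06 × 0.20 = 3.3, or 275 × 0.10 × 0.20 = 5.5.

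**The case against.** **The omission is inferred.** The code is offered as a sample, and the Table 5 wording could attach the new terms to the imputation. This stands as a limit, but the inference is strong. In an imputation run separately by arm, treatment is constant, so a treatment-by-ERIPD term can only belong to the ANCOVA. If ERIPD was meant to be in the imputation, the SAP needs to say so.

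**The plan may be right as written.** The estimand is treatment policy, and many subjects with missing values will have stopped the study product. If an ERIPD effect on the contrast exists only on treatment, imputing none is nearly correct and the obvious repair overshoots. This stands, and neither assumption can be tested with so few returners.

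**A reader might infer that the analysis hides an effect.** The figures do not support that. At 20% missing, adding ERIPD while keeping returner donors leaves the chance that the 90% CI excludes zero almost unchanged (38% against 37%), because the standard error rises. Fitting to all observed values does raise it, but that gain is the completers' ERIPD effect carried into the imputations, and it roughly matches a plain observed-data analysis (54% against 57% at 20% missing).

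**A reader might also infer that the equivalence claim is at risk.** It is not. Analysis 6 has no decision rule. Appendix 4 marks every listed inclusion and exclusion deviation as important, so the per-protocol set (Analysis 2) removes all such subjects, and PPS3 removes those judged to affect efficacy.

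**Conclusion.** The concern holds as a limited one, worth considering rather than essential. On the plain reading, Analysis 6 estimates an interaction that its imputed values cannot contain. If the ERIPD effect persists in subjects with missing Week 26 data and missingness is similar between arms, the estimate shrinks by about the missing fraction: 5% to 30% over the assumed range, and 31% to 35% in the two cases where ERIPD subjects are missing more often. At 10% missing that is only about 0.04 HbA1c points on a true 0.40.

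Shrinkage toward zero is the usual direction, not a rule. Unequal missingness between arms combined with an ERIPD main effect can create an interaction or enlarge one. All sizes depend on assumed missingness, ERIPD share and effect size. The conclusions on HbA1c equivalence and non-inferiority do not depend on this analysis.

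**What to change.** **Analysis 6 only.** State the imputation model and include ERIPD in it, by arm. Because returners with an ERIPD will be few, fit the by-arm regression to all observed Week 26 HbA1c values, with baseline HbA1c, ERIPD and an indicator for stopping treatment before Week 26, and set that indicator for the subjects being imputed. This keeps a shift for stopping treatment while letting imputed values carry an ERIPD effect. In simulation (6% returners, SD 0.9, effect persisting off treatment) it returned 0.40, 0.39 and 0.40 at 10%, 20% and 30% missing for a true 0.40. Report two further versions beside it: the interaction from observed Week 26 data, and the interaction from the imputation as now written.

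**Analysis 7.** Keep the completer-based imputation stated in Section 11.7.1.3 and add the subgroup variable to the by-arm imputation model.

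**Main analysis.** Leave it unchanged, including the returner-only donors adopted at FDA's suggestion.

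**Cost.** A few lines of SAP text and code, and two extra rows of output. The downside is that the new model assumes the same ERIPD effect on and off treatment, and it overstates the interaction if the effect exists only on treatment. That is why the three versions should be shown together.
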